CooperVision is evaluating the clinical performance of its Phoebe contact lenses (Test) compared to the commercially available MyDay contact lenses (Control) over 3-day of lens wear on a daily wear, daily disposable modality in a randomized, double masked, bilateral, cross-over dispensing study.

2 Study Objective

The purpose of this study is to validate the clinical performance of the Phoebe contact lenses.

The primary variable of interest is:

- Anterior ocular health examination

The secondary variable of interest is:

- Visual acuity and Vision quality

[REDACTED]

- [REDACTED]
- [REDACTED]
- [REDACTED]

2.1 Study Hypotheses

The primary study hypothesis is that the Phoebe contact lens performs substantially equivalent to the MyDay contact lens for ocular health.

The secondary study hypothesis is that The Phoebe contact lens is not inferior to the MyDay contact lens for vision and visual acuity.

[REDACTED]

- [REDACTED]
- [REDACTED]

[REDACTED]

3 Study Design

This will be a double-masked, randomized, bilateral, cross-over, 3-day dispensing study comparing the Phoebe Test lens against the MyDay Control lens. Each subject will be randomized to wear either the Test or Control lenses first as a matched pair. Each lens pair will be worn for 3 days. All lenses will be replaced daily.

It is anticipated that this study will involve up to 4 scheduled visits:

- Visit 0: Enrolment / Screening / Baseline Visit
- Visit 1: Dispensing of Pair 1
- Visit 2: Follow-up of Pair 1 (+2 days) and Dispensing of Pair 2
- Visit 3: Follow-up of Pair 2 (+2 days) and Exit

4 Ethics Review / Statement of Compliance

4.1 Relevant Standards / Guidelines

This implementation document has been developed in accordance with the following:

- ISO 14155 Clinical Investigation of Medical Devices for Human Subjects, 21CFR 812.2 (b) IDE-abbreviated requirement
- Declaration of Helsinki

4.2 Institutional Review Board

This study will be conducted in accordance with Institutional Review Board (IRB) regulations (U.S. 21CFR Part 56.103). Copies of all IRB/IEC correspondence with the investigator/sponsor will be kept on file.

The conduct of this study will be approved by an Institutional Review Board prior to commencement.

4.3 Informed Consent

Informed consent shall be obtained in writing from the subject and the process shall be documented before any procedure specific to the clinical investigation is carried out.

5 Clinical Trial Registration

This Study will be registered with ClinicalTrials.gov in accordance with Section 801 of the Food and Drug Administration Act (FDAA) which mandates the registration of certain clinical trials of drugs and medical devices.

6 Potential Risks and Benefits to Human Subjects

This study is considered to be a non-significant risk study based on United State Food and Drug administration (FDA) and International Standards Organization (ISO) guidelines due to the daily wear nature of the study and existing approvals from FDA for the MyDay control contact lens. The contact lenses used in this study are intended for daily wear (NOT extended wear) with usage consistent with typical daily wear.

The Phoebe test lens is manufactured with the same material as the MyDay control lens with a modified optical design, and should therefore not present increased risk to the patient.

There might not be direct benefits to the subjects in this study. However, participation in a study may contribute to scientific research information that may be used in the development of new contact lens products. In addition, subjects will receive an examination of the front part of their eyes and may have the opportunity to try a different type of soft contact lenses and/or different lens care products at no cost to them.

Complications that may occur during the wearing of contact lenses include discomfort, dryness, aching or itching eyes, excessive tearing, discharge, hyperemia and variable or blurred vision. More serious risks may include photophobia, iritis, corneal edema or eye infection. Although contact lens-related infections are very infrequent, the possibility does exist. The incidence of infection due to day-wear soft lenses is 0.035%. Almost always an infection will occur only in one eye. This risk is assumed by 35-million Americans who currently wear contact lenses.

Non-Invasive clinical procedures including auto-refraction, auto-keratometry, visual acuity, anterior ocular health assessment, and [REDACTED] will be used. [REDACTED]

There might not be direct benefits to the subjects in this study. However, participation in a study may contribute to scientific research information that may be used in the development of new contact

lens products. In addition, participants will receive an examination of the front part of their eyes and may have the opportunity to try a different type of soft contact lens and/or different lens care products at no cost to them.

7 Materials and Methods

7.1 Clinical sites

The study will take place at Indiana University School of Optometry, Clinical Optics Research Lab.

This site was selected based on the experience of the site investigators and staff in conducting clinical trials, the availability of potential study participants, and the interest of the site in performing the trial. A site investigator agreement and financial disclosure document will be in place prior to commencement of the trial.

7.2 Participants

Up to 80 subjects will be recruited for this study with the goal to have approximately 50 subjects to complete in total. Each subject will be given a unique ID number. Additionally, all subjects must meet the study inclusion and exclusion criteria listed below.

Inclusion criteria

A person is eligible for inclusion in the study if he/she:

- **Between and 18 and 35 years of age** and has full legal capacity to volunteer
- Has had a self-reported oculo-visual examination in the last two years
- Has read and understood the information consent letter
- Is willing and able to follow instructions and maintain the appointment schedule
- Is correctable to a visual acuity of 20/25 or better (in each eye) with their habitual correction or 20/20 best corrected
- Has a Contact Lens Refraction between -1.00D and -6.00D
- Cylinder power \leq **-0.75DC** in Spherical Cylindrical Refraction
- Currently wears soft contact lenses
- **Is willing to wear lenses for a minimal of 8 hours a day and everyday during the course of the study**
- Has clear corneas and no active ocular disease
- Has not worn lenses for at least 12 hours before the first visit

Exclusion Criteria

A person will be excluded from the study if he/she:

- Has never worn contact lenses before
- Is wearing Monovision modality
- Has any systemic disease affecting ocular health
- Is using any systemic or topical medications that will affect ocular health
- Has any ocular pathology or severe insufficiency of lacrimal secretion (moderate to severe dry eyes) that would affect the wearing of contact lenses
- Has persistent, clinically significant corneal or conjunctival staining using sodium fluorescein dye
- Has any clinically significant lid or conjunctival abnormalities, active neovascularization or any central corneal scars
- Is aphakic
- Has undergone corneal refractive surgery
- Is participating in any other type of eye related clinical or research study

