7.3 Study Materials

7.3.1 Contact lens

Subjects will be randomized to receive either the Test or Control lens as a matched pair at each visit per a predetermined randomization schedule. The lenses used in this study will be provided by the Sponsor.

The Test lens material is approved by the FDA and the Control lens is commercially available. However, both the Test and Control lenses will be labelled with “Investigational” wording on the labels for study masking purpose.

Details of the contact lenses are shown in Table 1.

| | Phoebe (Test) | MyDay (Control) |
|-----------------|------------------------------|------------------------------|
| Material | stenfilcon A | stenfilcon A |
| Manufacture | CooperVision | CooperVision |
| Base curve (mm) | 8.4 | 8.4 |
| Diameter (mm) | 14.2 | 14.2 |
| Power (D) | -1.00 to -6.00 (0.25D steps) | -1.00 to -6.00 (0.25D steps) |

Table 1: Study lenses

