7.4.2 Visit 1: Dispensing visit

Dispensing visit may occur on same day as Visit 0. In which case, steps 1,2 &3 are redundant.

1. Entrance distance HHHC VA (OD, OS) with best spherocylindrical correction.
2. Slit lamp biomicroscopy will be assessed according to the criteria set out in the Appendix 2.
 - a. Not required if done in combination with Visit 0.
3. The investigator will confirm that the patient meets the criteria set out in the inclusion criteria.
4. The first pair of lenses will be inserted by the subject according to randomization schedule.
5. Initial contact lens power chosen based on vertexed, spherical equivalent obtained from refraction.
6. The initial lens fit will be assessed for fit acceptance (acceptable or not acceptable). If the fit is acceptable, the subject will be allowed to sit in the waiting area for a minimal of 10 minutes to allow for the lenses to settle.
7. Visual acuity with initial contact lens power will be assessed.
 - a. Distance visual acuity
 - i. High Illumination High Contrast (OU)
 - ii. Low Illumination High Contrast (OU)
 - b. Near visual acuity
 - iii. High Illumination High Contrast (OU)
 - iv. Low Illumination High Contrast (OU)
8. After lens settling a standard distant monocular over-refraction will be performed. The endpoint of this over refraction will be the best objective acuity and subjective acuity improvement.
 - a. Up to -0.50D will be given if objective visual acuity is improved.
 - b. -0.25D will be given if subjective visual acuity is significantly improved.
9. A lens change will be implemented if over-refraction dictates. The replacement lens will be allowed to settle for 10 minutes.
10. Change lens prescription to that noted by over-refraction, if needed.
11. Visual Acuity will be assessed with the final lens powers.
 - c. Distance visual acuity
 - v. High Illumination High Contrast (OU)
 - vi. High Illumination Low Contrast (OD, OS, OU)

vii. Low Illumination High Contrast (OD, OS, OU)

d. Near visual acuity

viii. High Illumination High Contrast (OU)

ix. Low Illumination High Contrast (OU)

High Illumination: Overhead lights on, Ideal: 60cd/m², Range: 120-200cd/m²

Low Illumination: Overhead lights off, Ideal: Ideal: 3cd/m², Range: 1-5cd/m²

[REDACTED]

[REDACTED]

14. The subject will be instructed to wear lenses for a minimal of 8 hours/day and every day until the subject come back for the follow-up visit.

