 - ii. Low Illumination High Contrast (OU)

High Illumination: Overhead lights on, Ideal: 60cd/m², Range: 120-200cd/m²

Low Illumination: Overhead lights off, Ideal: Ideal: 3cd/m², Range: 1-5cd/m²

6. Monocular over-refraction and High Illumination High Contrast logMAR VA @ 4m (OU) will be performed and recorded.

8. Lens removal and lens storage.
9. Slit lamp biomicroscopy will be assessed set out in the CVI grading scales.
10. Exit distance HHHC logMAR visual acuity with refraction from baseline visit (OD, OS, OU)
11. Exit statement signed and exit disposition recorded.

7.4.5 Summary of Visits and Procedures for the study.

Table 2 summarizes the visits and procedures for the study.

Table 2: Summary of Visits and Procedures

| | Visit 0 Screening / Baseline | Visit 1 Dispense Pair 1 | Visit 2 Follow-up P1 / Dispensing of Pair 2 | Visit 3 Follow-up P2 & Exit |
|--------------------------------------|------------------------------------|-------------------------------|---|-----------------------------------|
| Informed consent | ✓ | - | - | - |
| Meet inclusion/exclusion criteria | ✓ | - | - | - |
| History at baseline/Demographics | ✓ | - | - | - |
| Wearing time | ✓ | - | ✓ | ✓ |
| Auto-refraction & keratomtery | ✓ | - | - | - |
| Pupilometer | ✓ | | | |
| Sphero-cylindrical refraction | ✓ | - | - | - |
| LogMAR VAs with spectacle refraction | ✓ | - | - | - |
| Slit-lamp biomicroscopy | ✓ | ✓* | ✓ | ✓ |
| Instillation of lens at office | - | ✓ | ✓ | - |
| ████████████████████ | █ | █ | █ | █ |
| ████████████████████ | █ | █ | █ | █ |
| ████████████████████ | █ | █ | █ | █ |
| Spherical over-refraction (SOR) | - | ✓ | ✓ | ✓ |
| LogMAR visual acuity | - | ✓ | ✓ | ✓ |
| ████████████████████ | █ | █ | █ | █ |
| Exit VAs | - | - | - | ✓ |
| Study Exit | - | - | - | ✓ |

* Not applicable if Visit 1 occurs on the same day as Visit 0

Calibration will be done on all applicable instruments (i.e., autorefractor and keratometer) prior to the start of the study and a copy of the calibration document will be kept on file. A copy of the calibration document will be forwarded to the Sponsor.

8 Adverse Event Reporting

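### The cylinder inclusion limit is a signed inequality that, read literally, admits only eyes with 0.75 D or more of minus cylinder, with no maximum, and excludes lower cylinder

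*Combined protocol and SAP*

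**What the plan says.** The inclusion list in section 7.2 contains the line "Cylinder power \leq -0.75DC in Spherical Cylindrical Refraction". The limit thus applies to the cylinder found "in Spherical Cylindrical Refraction". The same section makes the list binding: "all subjects must meet the study inclusion and exclusion criteria listed below". The neighbouring refractive criterion also uses signed dioptres: "Has a Contact Lens Refraction between -1.00D and -6.00D".

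Three other places bear on what the cylinder line can sensibly mean:

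- **Section 7.3.1, Table 1** gives each study lens one power range, -1.00 to -6.00 D in 0.25 D steps, with no cylinder or axis.
- **Section 7.4.2, step 5** says "Initial contact lens power chosen based on vertexed, spherical equivalent obtained from refraction". Section 7.4.3, step 12, repeats this for the second pair.
- **Section 7.4.5, Table 2** labels the over-refraction at Visits 1 to 3 as spherical.

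Section 11.5 names enrolment outside the inclusion and exclusion criteria among the deviations that must go to the IRB.

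**The concern.** On the minus-cylinder scale, more astigmatism means a more negative number. A less-than-or-equal sign in front of a negative value therefore sets a minimum amount of astigmatism, not a maximum. The line carries no word such as magnitude, absolute or up to that would reverse this.

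Two things are at stake, depending on how the line is applied:

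- **Literally.** The trial would recruit only eyes with at least 0.75 D of cylinder and fit them with lenses that do not appear to correct it. The visual acuity comparison, which carries the secondary non-inferiority hypothesis in section 2.1, would be made with uncorrected astigmatism present under both lenses.
- **As probably intended.** The right eyes are enrolled, but every subject with 0.00 to -0.50 DC fails the written criterion, and section 11.5 makes that failure reportable.

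**Working it through.** There is no sample size, power or alpha figure to reproduce here. The check concerns the direction of an inequality and its consequence for a lens fitted to the spherical equivalent.

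**Inputs.** The threshold of -0.75 DC and the less-than-or-equal sign come from section 7.2. The lens powers, -1.00 to -6.00 D, come from section 7.3.1. The spherical-equivalent rule comes from sections 7.4.2 and 7.4.3. The cylinder values 0.00 to -3.00 DC in 0.25 D steps, and the -3.00 D sphere used below, are illustrative choices, not figures from the plan.

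**Step 1: who is admitted.** Let c be the signed cylinder.

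| Reading | Admitted | Refused |
|---|---|---|
| As written, c ≤ -0.75 | -0.75, -1.00, … -3.00 and beyond | 0.00, -0.25, -0.50 |
| Magnitude, absolute c ≤ 0.75 | 0.00, -0.25, -0.50, -0.75 | -1.00 and beyond |

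The two readings agree only at exactly -0.75 DC. If refraction were recorded in plus-cylinder form, no eye would satisfy the line as written.

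**Step 2: does another criterion cap cylinder?** No.

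- The refraction range of -1.00 to -6.00 D does not mention cylinder.
- The acuity criterion reads "Is correctable to a visual acuity of 20/25 or better (in each eye) with their habitual correction or 20/20 best corrected". An eye with high but well-corrected astigmatism can meet its second limb.
- No exclusion criterion refers to astigmatism.

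**Step 3: what a lens fitted to the spherical equivalent leaves uncorrected.** The spherical equivalent is S + c/2, where S is the sphere. The error left in the two principal meridians is ± (absolute c)/2. Vertex adjustment is ignored.

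| Refraction | Spherical equivalent | Error left per meridian | As written | Magnitude |
|---|---|---|---|---|
| -3.00 / -0.50 | -3.00 - 0.25 = -3.25 D | ±0.25 D | refused | admitted |
| -3.00 / -0.75 | -3.00 - 0.375 = -3.375 D | ±0.375 D | admitted | admitted |
| -3.00 / -2.00 | -3.00 - 1.00 = -4.00 D | ±1.00 D | admitted | refused |
| -3.00 / -3.00 | -3.00 - 1.50 = -4.50 D | ±1.50 D | admitted | refused |

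All four spherical equivalents lie within the lens power range, so lens availability would not screen out the high-cylinder eyes. The literal line refuses the eye with the least uncorrected error and admits those with the most.

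**Step 4: set against the rest of the plan.** Single-power lenses, spherical-equivalent fitting and spherical over-refraction all suit eyes with little cylinder. The eligibility line, as written, selects the reverse.

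**The case against.** The strongest reply is that this is a notation slip whose intent is plain. The lens table and fitting rule make little sense unless low astigmatism is wanted. The only site is an optometry school, chosen in part for its experience with trials, and an optometrist would probably read the line as no more than 0.75 D. This stands: actual enrolment may well be unaffected, and the point is a drafting error rather than a poor design choice. It does not remove the problem, because a monitor checking eligibility against the text would reach the opposite answer.

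A reader might infer that literal application would make non-inferiority on acuity easier to show, because shared blur masks a difference between optical designs. The documents do not support a direction. In this crossover the same eyes are measured under both lenses. Residual cylinder could compress a lens difference, but it could also make acuity more variable and widen the paired interval, which works the other way. The readable text gives neither a margin nor a standard deviation with which to settle it.

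A reader might also set the ±1.00 D left by a -2.00 DC eye against the 0.50 D over-refraction allowance in section 7.4.2. The two are not comparable: the allowance is extra minus spherical power, and a spherical change does not correct cylinder.

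Finally, the IRB point can be called formalism. Nothing shows that the sponsor, site or IRB would in fact treat a -0.50 DC eye as ineligible. The consequence claimed is only what follows from the words of sections 7.2 and 11.5.

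**Conclusion.** The criterion is wrong as written: it is a drafting error in an eligibility threshold that applies to every subject. Literally, it excludes 0.00 to -0.50 DC, sets no maximum, and shares only -0.75 DC with a 0.75 D limit on magnitude. Its practical weight is low to moderate because the site would probably apply the intended meaning. In that case what remains is a mismatch between the text and the eyes enrolled, reportable on the literal wording.

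The documents do not support a claim that the vision conclusion is biased in a known direction or by a known amount. No effect is claimed on the primary variable, the anterior ocular health examination.

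The conclusion rests on two assumptions. First, the minus sign and inequality are as printed; the line is not redacted. Second, both lenses are spherical. That is inferred from the single power in Table 1 and the spherical-equivalent fitting, since the documents do not use that word for the lenses.

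**What to change.** The sponsor should confirm the intent and restate the limit as a magnitude with both ends given. If low astigmatism is meant, the line would say that the absolute cylinder is no more than 0.75 D, that is, 0.00 to -0.75 DC. The eligibility form should carry the same wording, so that the Visit 0 check and the repeat check at Visit 1 use one rule.

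The cost is one line of protocol text and the matching line on the form, with no added subjects, visits or procedures.

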7.3 Study Materials

7.3.1 Contact lens

Subjects will be randomized to receive either the Test or Control lens as a matched pair at each visit per a predetermined randomization schedule. The lenses used in this study will be provided by the Sponsor.

The Test lens material is approved by the FDA and the Control lens is commercially available. However, both the Test and Control lenses will be labelled with “Investigational” wording on the labels for study masking purpose.

Details of the contact lenses are shown in Table 1.

| | Phoebe (Test) | MyDay (Control) |
|-----------------|------------------------------|------------------------------|
| Material | stenfilcon A | stenfilcon A |
| Manufacture | CooperVision | CooperVision |
| Base curve (mm) | 8.4 | 8.4 |
| Diameter (mm) | 14.2 | 14.2 |
| Power (D) | -1.00 to -6.00 (0.25D steps) | -1.00 to -6.00 (0.25D steps) |

Table 1: Study lenses

7.3.2 Contact Lens care

No contact lens care is required for this study as lenses are to be worn for a single day only. Subjects are allowed to use saline solution for rinsing purpose as needed. The saline solution will be provided to subject by the clinical site. Subject's habitual rewetting drdrops may be used if needed.

7.3.3 Storage of Lenses and Lens Care Solutions

The study materials must be stored in a secured area. All lenses and lens care solutions should be stored at controlled room temperature (59-86°F).

7.3.4 Clinical Supply Inventory

The investigator must keep an accurate accounting of the study product during the study. A detailed inventory must be completed for study supplies. The study supplies are to be used in accordance with the implementation document by subjects who are under the direct supervision of an investigator.

7.3.5 Disposal of Consumables

This study dispenses consumables (lenses) to participants for use during the study. Participants will be instructed to dispose of worn lenses (both test and control lenses) daily. However, participants will be instructed to retain and return "problem" lenses. Study lenses worn by participants on the follow-up visits will be collected and returned to the sponsor at the completion of the study. Worn lenses will be stored in saline solutions. All unworn lenses will also be returned to the sponsor.

7.3.6 Masking and Control of Study Materials

The contact lenses coding will be masked to both the investigator and subject.

7.3.7 Ordering and Accountability of Study Materials

The test and control lenses will be provided by the sponsor.

The investigator must complete an accurate accounting of the study product at the completion of the study. A detailed inventory must be completed for study supplies.

All unused will be returned to the Sponsor at the end of the study unless the investigator is otherwise directed by the study Sponsor. Worn lenses on the last day of each lens type will be returned to the Sponsor.

7.4 Visit Schedule and Procedures

7.4.1 Visit 0: Baseline /Screening Visit

Procedures to be Performed

The following evaluations will be performed to assess eligibility according to the Inclusion and Exclusion Criteria at the baseline visit only:

1. The patient is expected to attend the baseline visit not wearing their habitual contact lens products.
 2. The subject will be required to read and sign an Informed Consent Form prior to enrolment. When the subject has signed the consent form, the subject will be considered to be enrolled on to the study.
 3. Participant demographics (age, sex, medications, allergies) will be recorded.
 4. Habitual lens wearing time (average, maximum, average comfortable) will be recorded.
 5. [REDACTED]
 6. Auto Refraction/Auto Keratometry: steepest and flattest K readings (mm).
 7. Pupil Sizes in High and Low Illumination will be measured using the Neuroptics pupilometer while looking in the distance.
 8. Sphero-cylindrical refraction will be conducted
 9. Visual Acuity will be assessed with be assessed with Sphero-cylindrical refraction (D)
 - a. Distance visual acuity
 - i. High Illumination High Contrast (OU)
 - ii. High Illumination Low Contrast (OD, OS, OU)
 - iii. Low Illumination High Contrast (OD, OS, OU)
 - b. Near visual acuity
 - i. High Illumination High Contrast (OU)
 - ii. Low Illumination High Contrast (OU)
- High Illumination: Overhead lights on, Ideal: 60cd/m², Range: 120-200cd/m²
- Low Illumination: Overhead lights off, Ideal: Ideal: 3cd/m², Range: 1-5cd/m²
10. Slit lamp biomicroscopy will be assessed according to the guidelines set out in the CVI Grading scales.

11. The investigator will confirm that the patient meets the criteria set out in the inclusion criteria.

